10. MONITORING

10.1 Data Safety Monitoring Plan

The Clinical Trial Monitor from the Michigan Institute of Clinical Health Research (MICHR) will set up a monitoring plan to include scheduled and as needed in person and remote monitoring visits to confirm the accuracy of study data, review study documents (including informed consents), and assess compliance with human subjects research.

10.2 Independent Medical Monitor

This study also has an assigned medical monitor who is not part of the study team ([name]). The primary responsibilities of the Medical Monitor include:

1. Provide feedback for protocol changes, if needed
2. Review/provide written feedback/sign off on captured AEs and withdrawals annually (in aggregate, to coincide with annual IRB continuing review)
3. Review/provide verbal feedback/sign off SAEs/unanticipated problems as they arise, depending on relatedness of the intervention
4. Assist with decisions about treatment withdrawal or dose reduction, on a case by case basis as they arise, for AEs thought to be probably related or definitely related to one of the interventions, regardless of expectedness.

10.3 Monitoring Plan and Information

To assure adequate protection of the rights of human subjects, per 21 CFR 312.50 and 312.53, the study will be monitored to ensure that the study is implemented in accordance with the protocol and applicable federal and local regulations, that proper informed consent procedures were followed and to insure the integrity and quality of the data.

A qualified trial monitor will be selected, per 21 CFR 312.53(d) to monitor this multi-site trial in accordance with the protocol and all applicable regulatory requirements. A monitoring plan will be established to ensure the quality and integrity of the data through pre-investigation, periodic site visits (both sites), review of adverse events/subject records, etc. The Michigan Institute for Clinical and Health Research (MICHR) will assist with the selection and support of the monitor assigned for this proposed clinical investigation and prepare the monitoring plan.

11. DATA HANDLING AND RECORD KEEPING

11.1 CRFs / Electronic Data Record

CRFs, in paper or electronic format, will be utilized and maintained by the study staff. Entries made in the CRF must be verifiable against source documents, unless the CRF is considered to be the source document.

11.2 Record Retention

Per 21 CFR §312.62, study records will be retained for a minimum of 7 years after the investigation is discontinued.

12. ETHICS

12.1 Institutional Review Board

Prior to study commencement, the study will be reviewed and approved by the Institutional Review Board (IRBMED, University of Michigan, Ann Arbor, MI).

12.2 Subject Information and Consent

A study team member will explain to each subject the nature of the study, its purpose, the procedures involved, the expected duration, the potential risks and benefits involved and any discomfort it may entail. Each subject will be informed that participation in the study is voluntary and that he/she may withdraw from the study at any time and that withdrawal of consent will not affect his/her subsequent medical treatment or relationship with the treating physician.

This informed consent will be given by means of a standard written statement, written in non-technical language. The subject should read and consider the statement before signing and dating it, and should be given a copy of the signed document. No patient can enter the study before his/her informed consent has been obtained.

The informed consent form is considered to be part of the protocol, and will be submitted for IRB approval.

13. STUDY DISCONTINUATION CRITERIA

Treatment Stopping Rules for Safety Reasons

1. Any SAE, as defined in section 8.2.
2. Psychosis, severe/uncontrolled depression, or increased suicidality. Participant behavior or comments that suggest imminent threat of suicide will prompt immediate 911 activation. Behavior or comments that suggest suicide ideation with plan but no immediate threat will prompt psychiatric ER referral

3. Participants who demonstrate physical, emotional, or behavioral signs that are thought to be probably related or definitely related to one of the interventions, and in whom dose adjustments have failed* or are not an option

Modafinil Specific Stopping Rules for Safety reasons

1. Pregnancy.
2. Suspected allergic reactions: rash, hives, mouth sores, blisters, swelling of your face, eyes, lips, tongue, or throat, trouble swallowing or breathing, fever, shortness of breath, swelling of the legs, yellowing of the skin or whites of the eyes, or dark urine.
3. Participants who decide to start another fatigue treatment medication (stimulant or wake-promoting agent) such as amantadine (Symmetrel), modafinil (Provigil), short or long acting methylphenidate (Ritalin/Concerta), dextroamphetamine (Dexedrine), dextroamphetamine-amphetamine (Adderall, Adderall XR), lisodexamfetamine (Vyvanse), armodafinil (Nuvigil), or amphetamine (Adzenys XR-ODT, Dyanavel XR, and Evekeo) amantadine, methylphenidate, or amphetamine during the study.

* Participants who experience intolerable but common side effects associated with modafinil (headache, nausea, nervousness, rhinitis, diarrhea, back pain, anxiety, insomnia, dizziness, and dyspepsia), that do not fulfill SAE criteria, will be required to stop modafinil at the dose which was associated with the symptoms, but upon improvement of symptoms, may be allowed to restart the medication at ½ of the dose that previously led to prior symptoms. Participants who still continue to experience symptoms after a re-challenge with ½ dose modafinil will be instructed to discontinue modafinil.

Off-Study Criteria

For participants who must have modafinil withdrawn for safety or ineligibility will still be encouraged to stay in the study for observation (and ongoing CBT, for combination treatment group) until completion unless they choose not to.

Discontinuation of a Subject

In the event a patient drops out of the study or is lost to followup, all attempts will be made to exit the patient in accordance with the protocol requirements. The reason for discontinuation (and the person who decided that discontinuation was necessary) will be recorded.

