All potential risks of modafinil will be outlined in the informed consent document and discussed with the patient prior to enrollment. Patients will also be advised that there may be unforeseen risks not outlined in the ICF. Based on the package insert, eligibility criteria will exclude pregnant women, and a urine pregnancy test will be required prior to study enrollment. Women of childbearing age will be advised of the risk of decreased effectiveness of hormonal contraception with modafinil use and be advised to use a form of birth control that does not involve hormonal contraception (spermicide or condoms) during the study and for one month after discontinuation of modafinil treatment. Participants with a history of hepatic impairment, participants over age 65, and participants who use warfarin, phenytoin, MAOIs and cyclosporine will be given dose limitations that will not exceed half of the maximal daily dose for healthy patients (50-100 mg once-twice daily as tolerated). Patients will be advised to monitor for common side effects of modafinil including headache, nausea, nervousness, rhinitis, diarrhea, back pain, anxiety, insomnia, dizziness, and dyspepsia while on modafinil, and if these symptoms occur or worsen, to alert the study team, during which time dose reduction or discontinuation will be discussed. Participants who experience worsening depressive symptoms, psychosis, increased suicidality, or suspected allergic reactions (rash, hives, mouth sores, blisters, swelling of the face, eyes, lips, tongue, or throat, trouble swallowing or breathing, fever, shortness of breath, swelling of the legs, yellowing of the skin or whites of the eyes, or dark urine) will be instructed to stop treatment immediately and contact the study team. Participants are also advised not to consume alcohol per the drug label. Participants should be instructed to call study team when new drugs are added or removed from their drug regimens so that drug interactions can be assessed. Participants may choose to discontinue their treatment at any time if they experience any untoward effects that they believe are related to modafinil, but will be encouraged to remain in the study until completion for monitoring. Adverse events and severe adverse events will be assessed/reported regularly and on an as-needed basis in accordance with the protocol, GCP, and IRB standards (see sections 7.5 and 8). Action involving possible PI discontinuation of study drug will be determined promptly in accordance with the protocol, GCP and IRB guidelines, as well as the medical monitor (see section 10 and 13).

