- If the 100 mg/day dose provides insufficient relief of fatigue, participants may increase the dose to 200 mg/day (upon awakening).
- If the 200 mg/day dose is adequate, but of insufficient duration, participants will be allowed to take another 1 or 2 pills around lunchtime (early afternoon: at least 8 hours before bedtime) for a total dose of 300 mg or 400 mg a day (max dose = 400 mg per day).
- If the 100 mg dose is perceived by the participant to be helpful with fatigue, but associated with excessive side effects (see 1.3), participants will be allowed to decrease their dose to 50 mg, once or twice daily, depending on duration of effect. A pill cutter will be provided by the study team if necessary.

*Participants who report a history of liver problems, participants age 65 or older, participants who use warfarin, phenytoin, MAOIs or cyclosporine†, and participants in whom the investigators think could be at increased risk for side effects, will only be permitted to take ½ of the maximum daily dose, prescribed enough pills to take a maximum of 1 pill twice a day (200 mg/per day) unless they have previously tolerated and required a higher dose prior to enrolling (in which case they will be allowed to return to their previously tolerated dose, up to 400

mg per day) . At baseline, these participants will be prescribed the 100 mg pills. They will be advised to take 50 mg once a day (upon awakening) as a starting point for the first week (A pill cutter will be provided by the study team if necessary.). Depending on results, participants will be allowed to adjust their dose based on the following scenarios:

- If the 50 mg/day dose effectively treats fatigue throughout the day, participants will remain on this dose.
- If the 50 mg/day dose is adequate, but of insufficient duration, participants will be allowed to take another ½ pill around lunchtime (early afternoon: at least 8 hours before bedtime) for a total dose of 50 mg twice a day.
- If the 50 mg/day dose provides insufficient relief of fatigue, participants may increase the dose to 100 mg/day (upon awakening).
- If the 100 mg/day dose is adequate, but wears off more quickly than desired, participants will be allowed to take another half pill or full pill around lunchtime (early afternoon: at least 8 hours before bedtime) for a total dose of 150 mg or 200mg a day (max dose = 200 mg per day).

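### Sections 5.3 and 13 give conflicting instructions for common modafinil side effects at 100 mg, and the section 13 half-dose rule cannot be carried out at 50 mg with the tablets described

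*Combined protocol and SAP*

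**What the plan says.** Section 5.3 (Interventions, Modafinil) starts standard participants on 100 mg once daily, using 100 mg pills that may be split, and lists the situations in which they may change dose. One of these concerns side effects. It covers a participant who finds 100 mg helpful but has excessive side effects, and it refers to section 1.3. In that case "participants will be allowed to decrease their dose to 50 mg, once or twice daily, depending on duration of effect". No interruption is mentioned, and symptoms need not improve first. A separate list covers higher-risk participants, who start on 50 mg once daily. It has four scenarios, none of them for side effects.

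The footnote in section 13 begins "Participants who experience intolerable but common side effects associated with modafinil" and applies when the event is not serious. Such participants "will be required to stop modafinil at the dose which was associated with the symptoms". Once symptoms improve they "may be allowed to restart the medication at ½ of the dose that previously led to prior symptoms". Anyone not free of the side effects at half dose is told to discontinue. The footnote is attached to treatment stopping rule 3, which applies once adjusting the dose has not worked or cannot be done.

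Section 1.3 tells participants, "if these symptoms occur or worsen, to alert the study team, during which time dose reduction or discontinuation will be discussed". The same paragraph refers possible discontinuation by the PI to sections 10 and 13. Section 10.2 has the medical monitor help with withdrawal or dose reduction in individual cases, for events probably or definitely related to treatment.

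**The concern.** A participant on 100 mg with troublesome headache or insomnia falls under both 5.3 and section 13. One section permits an immediate reduction that rests on the participant's own perception. The other requires a stop and makes any restart conditional. The two sites could read the same event differently, and participants could receive conflicting safety instructions.

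The statistical stake lies in Aim 3, which compares adverse events, side effects, adherence and dropout between arms, with adherence measured as the percentage of prescribed therapy used. An enforced interruption and a direct step-down can give different recorded usage for the same event.

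**Working it through.** No sample-size or power figure is involved. The check compares the passages and does simple dose arithmetic.

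**1. Do the passages cover the same symptoms?** Yes. Section 5.3 points to the list in 1.3, and section 13 repeats that list: headache, nausea, nervousness, rhinitis, diarrhea, back pain, anxiety, insomnia, dizziness and dyspepsia (ten in both).

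**2. Side by side.**

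| | Section 5.3 | Section 13 footnote |
|---|---|---|
| Trigger | *excessive*, with 100 mg perceived as helpful | *intolerable*, not serious, any dose |
| First action | permitted decrease to 50 mg once or twice daily | mandatory stop |
| Condition for the lower dose | none stated | symptoms have improved, and restart is allowed |
| If symptoms continue | not stated | discontinue |

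Section 8.4 grades events as mild, moderate or severe, but neither trigger word is tied to it.

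**3. A participant on 100 mg once daily.** Section 13 gives 0 mg until improvement, then ½ × 100 = 50 mg. Section 5.3 gives, without a break, either 50 mg/day or 2 × 50 = 100 mg/day. The second option leaves the daily total unchanged. If half means the daily dose, the sections end at different totals (100 against 50 mg/day). If it means the single dose, both reach 50 mg per intake, and they still differ on the interruption and on who decides.

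**4. A participant at 200 mg/day who is stopped and re-challenged.** With half taken as half the daily total, ½ × 200 = 100 mg. If 100 mg helps but symptoms continue, section 13 requires discontinuation. The 5.3 bullet for 100 mg permits 50 mg.

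**5. A higher-risk participant on the 50 mg once-daily start.** Section 5.3 offers no side-effect step. Section 13 gives ½ × 50 = 25 mg on either reading of dose. That is below every dose in 5.3. The smallest piece 5.3 describes is half of a 100 mg pill, which is 50 mg, and 25 / 50 = 0.5 of such a piece.

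**6. Half of each daily total that 5.3 permits.** 50→25, 100→50, 150→75, 200→100, 300→150, 400→200 mg. All except 25 and 75 mg can be made from 50 mg pieces. The 75 mg problem arises only if dose means the daily total. The 150 mg total is taken as 100 + 50 mg, and halving the 100 mg intake gives 50 mg, which can be made.

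**7. Number exposed.** Section 4.0 plans 330 enrolled, randomized 1:1:1, with modafinil in two of three arms: 330 × 2/3 = 220. The documents do not say how many of these would have an excessive or intolerable effect. The 5% that 1.3 attaches to common reactions in earlier trials is not such a rate.

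**The case against.** The best defence is that the passages form a sequence. *Excessive* could be the milder state, handled by the 5.3 step-down, and *intolerable* the worse one, handled by section 13. The link to stopping rule 3 supports this, because stopping there follows failed dose adjustment. The medical monitor can also help in individual cases, and 1.3 sends discontinuation decisions to sections 10 and 13. Doses are adjusted by participants as tolerated, so varying exposure is part of the design.

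This reading is possible, but the protocol does not state it. Neither word is defined. The footnote speaks of restarting after improvement, so it cannot simply mean moving to a lower dose. The monitor assists, and section 10.2 does not say whether 5.3 or 13 governs. The reference in 1.3 concerns discontinuation by the PI, not the participant-led decrease.

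The defence does rule out several stronger readings.

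- A reader might infer that 1.3 is a third conflicting rule. It calls only for a discussion of reduction or discontinuation, which fits either of the others.
- A reader might infer that some participants would be withdrawn outright depending on the page followed. For common non-serious effects, discontinuation is the last step of section 13's own sequence or a discussed option in 1.3. Those taken off modafinil are encouraged to stay in the study.
- A reader might infer a conflict at the top of the dose range, for example at 400 mg/day. The 5.3 scenarios above 100 mg are upward steps for insufficient effect or duration. They contain no side-effect step-down to contradict section 13.

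**Conclusion.** The contradiction is real but narrow. It is direct at 100 mg, including a re-challenge at 100 mg after 200 mg/day when 100 mg is perceived as helpful. At the 50 mg start for higher-risk participants the problem is different: 5.3 is silent, and the section 13 half dose cannot be made from half-tablets. Above 100 mg the fault is a gap in 5.3 and an undefined half, not a conflict.

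Up to about 220 participants work under these instructions, but the number whose dose path would differ cannot be estimated from the documents. Aim 3 adherence and side-effect results could be affected by an amount that cannot be sized. A reader might infer damage to the primary comparison, since section 6.6 ties the Week 12 survey and home monitoring to the last modafinil day. The documents do not show any effect on the MFIS change, and none is claimed here. This is a contradictory safety instruction that should be corrected. It is not a threat to the trial's main inference.

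**What to change.** Reconcile 5.3 with the section 13 footnote into one rule used at both sites, and have 1.3 and 10.2 refer to it. The rule should:

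- define *excessive* and *intolerable*, for instance against the severity scale in 8.4, or replace them with one term;
- say whether treatment is interrupted or reduced directly;
- say whether half means the single or the daily dose;
- cover every daily total in 5.3 (50, 100, 150, 200, 300 and 400 mg) and the higher-risk schedule, giving each resulting dose in whole or half 100 mg tablets, or saying that none is available;
- say how many attempts come before discontinuation.

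The clinical team decides which rule stands, and this review takes no view on it. The cost is protocol wording and a short site memo, with no added visits or participants.

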14. ENGAGEMENT

All patient stakeholders and study team members will participate in regular in-person or webinar meetings. At these meetings, aspects of the study will be reviewed, including study protocol and progress, interim regulatory issues, patient recruitment/enrollment/retention reports, operational issues, adverse events, and treatment adherence. Stakeholders and study team will mutually decide if strategic changes are required, and if so, will require stakeholder approval.

Stakeholders will:

- Participate in study monitoring. If milestones are not met, or are not likely to be met based on current methods, stakeholder feedback will be solicited to enhance delivery of milestones.
- Assist with distribution of recruitment materials.
- Assist with solicitation of clinic patients.
- Participate in development of a pre-screening procedure so that all potentially-eligible patients are identified in a standardized fashion.
- Be involved in authoring and reviewing dissemination materials.

